6.1.2 Ibrutinib Administration

Ibrutinib will be administered orally. Doses should be taken at the same time each day without regard to food or drink (except as noted in Section 6.6.2). Ibrutinib should be swallowed whole with water and the tablets should not be opened, broken, or chewed. A Medication Diary will be provided to the patient to record each date and dose of ibrutinib (Appendix IV).

If a dose of ibrutinib is not taken at the scheduled time, it can be taken as soon as possible up to 8 hours after the scheduled time on the same day with a return to the normal schedule the following day. If a patient does not take a dose within 8 hours of the scheduled time, that day's dose will be skipped. Extra capsules of ibrutinib should not be taken to make up for the missed dose. If the patient vomits after taking a dose, the patient should not repeat the dose but should resume dosing at the time of the next scheduled dose.

6.2 Phase I Treatment Administration

Patients will be enrolled to the phase I study through a standard 3 + 3 design. Eligible patients will include ibrutinib-naïve patients as well as selected ibrutinib-pretreated patients. Given the focus of the phase I study on safety/tolerability, patients who have progressed on ibrutinib that are felt to be at high risk for rapid progression on this study shall not be eligible for the phase I portion of the study (Eligibility Criteria 3.4). This exclusion of rapid progressors is designed to decrease the risk of having to replace multiple patients due to progression during the dose-limiting toxicity (DLT) assessment period.

Dose escalation shall occur according to Table 6-1. The first three patients shall be accrued to Dose Level 1 (3 mg ixazomib and 560 mg ibrutinib). Patients shall take ibrutinib continuously once daily of a 28 day cycle. Ixazomib will be administered orally on days 1, 8, and 15 of a 28 day cycle. Patients shall continue therapy until progression or unacceptable toxicity.

Table 6-1 Dose Levels for Phase I Study

Dose Level	Ixazomib Days 1, 8, 15 of a 28 Day Cycle	Ibrutinib Days 1-28 of a 28 Day Cycle
-1	3 mg	420 mg
1 Starting Dose	3 mg	560 mg
2	4 mg	560 mg

The MTD/RP2D shall be defined as the highest dose level where 0 or 1 out of 6 patients experiences a DLT. The first 3 patients will be accrued to Dose Level 1. If 0 of the first 3 patients enrolled experience a DLT, then the following cohort of 3 patients will be accrued to the next highest dose level. If 1 of the first 3 patients experience a DLT, then an additional 3 patients will be accrued at the current dose level. If 2 or 3 of the first 6 patients experience a DLT, then that dose level shall be considered too toxic and dosing will occur at Dose Level (-1). If 2 or 3 patients experience a DLT at Dose Level (-1), the regimen will be considered too toxic and the trial will end. If Dose Level 2 proves safe (0 or 1 DLT's out of 3 patients), then an additional 3 patients shall be accrued to Dose Level 2. If 0-1 out of 6 total patients treated at Dose Level 2 experience a DLT, then that dose level shall be considered the RP2D and the phase 1 study shall end. There shall be no dose escalation above Dose Level 2. If 2 or 3 patients in Dose Level 2 experience a DLT, then that dose level shall be considered too toxic and Dose Level 1 shall be considered the RP2D as long as 0 or 1 out of 6 patients experiences a DLT.

Patients may delay therapy (ibrutinib and/or ixazomib) up to 1 week in Phase I, Cycle 1. In this case, subsequent doses of ixazomib must be >72 hours from the prior dose. As a result, for Phase I, Cycle 1 only, patients who delay a dose due to toxicity may delay subsequent doses up to 1 week to allow for at least a 3 day period between doses of ixazomib.

Patients on Phase I, Cycle 2 and subsequent cycles shall not make up any ixazomib doses that are delayed >72 hours due to toxicity (missed doses can be taken as soon as the patient remembers if the next scheduled dose is 72 hours or more away).

For Cycle 1, patients should receive all ixazomib doses in clinic after a provider assessment. For all subsequent cycles, patients are only required to be seen in clinic on day 1 of the cycle (**NOTE:** Cycle 2 and Cycle 3, Day 15 (and Day 22, if applicable) mandatory blood counts can be done locally).

Three patients were enrolled to Dose Level 1 with no DLTs during the 28 day assessment period. Nine patients were enrolled to Dose Level 2. Five of the nine patients completed the 28 day assessment period with no DLTs, and one patient experienced a Grade 3 lung infection that was considered a DLT. Three of the nine patients were not evaluable for DLT and were replaced. One patient was inadvertently given neulasta prior to receiving Cycle 2, Day 1 therapy; another patient unintentionally took Day 15 ixazomib on Day 9; and one patient forgot to take ibrutinib the last 8 days of Cycle 1 unrelated to any toxicities. **Phase I was completed November 25, 2019. Dose Level 2 is the recommended Phase 2 dose.**

6.2.1 DLT Assessment

Patients shall be assessed for DLT through the conclusion of Cycle 1 (i.e., prior to Cycle 2, Day 1). Patients experiencing progression or who are non-adherent to the study regimen and/or assessments will be removed from study therapy and replaced for the purposes of DLT assessment. Patients who miss 5 consecutive

doses of ibrutinib for reasons unrelated to toxicity OR who experience a dose delay of ixazomib of >72 hours for reasons unrelated to toxicity will not be considered DLT's. These patients shall be replaced for the purposes of DLT assessment and determination of the MTD/RP2D but may continue study therapy at the discretion of the investigator. DLT shall be defined according to Table 6-2. Patients who experience a DLT, may continue on study therapy. DLTs shall be managed according to Section 6.5 detailing dose modifications/delays and patient can re-start therapy once they meet criteria noted in Section 6.4.

Table 6-2 Dose Limiting Toxicities for Phase I

	Any toxicity-related dose delay >7 days of ibrutinib or ixazomib or inability to complete 3 doses of ixazomib within the first cycle due to toxicity shall constitute a DLT. A delay of >7 days of the start of Cycle 2 due to toxicity shall also constitute a DLT.
Grade 3	Non-Hematologic Toxicity aside from Grade 3 diarrhea, nausea, or vomiting which resolve within 48 hours of supportive care.
Grade 3	Thrombocytopenia with significant bleeding (defined as acute bleeding requiring a transfusion and/or hospitalization).
Grade 4	Thrombocytopenia
Grade 4	Febrile Neutropenia lasting longer than 7 days. To meet criteria for DLT, patients must remain febrile and neutropenic for >7 days. If a patient remains neutropenic but the fever resolves within 7 days, it shall not constitute a DLT.
Grade 4	Non-Hematologic Toxicity
Grade 5	Any Toxicity

6.3 Phase II Treatment Administration

Once the MTD/RP2D is determined, the phase I portion of the study shall end and the phase II portion shall begin (**Phase I completed November 25, 2019**). For the phase II portion of the study, patients will be divided into two cohorts: BTK-pretreated and BTK-naïve. All patients who have received one dose of ibrutinib or any BTK inhibitor or more shall be assigned to the BTK-pretreated cohort. **August 7, 2020: BTK-pretreated cohort closed.**

Patients shall receive therapy at the RP2D: Ibrutinib 560 mg and Ixazomib 4 mg, with ibrutinib administered continuously daily and ixazomib administered on days 1, 8, and 15 of a 28 day cycle. Patients shall continue therapy until they have evidence of progression or unacceptable toxicity or withdrawal of consent.

Patients shall not make up any ixazomib doses that are delayed >72 hours due to toxicity (missed doses can be taken as soon as the patient remembers if the next scheduled dose is 72 hours or more away).

For Cycle 1, patients should receive day 1 and day 15 ixazomib doses in clinic after a provider assessment. For Cycle 2-7, patients are only required to be seen in clinic on day 1 of the cycle.

If patients continue on study therapy after Cycle 6, patients are required to be seen in clinic every 12 weeks (Day 1 of every 3 cycles) starting with Cycle 7.

6.4 Criteria to Begin a New Cycle of Therapy

Prior to starting a new cycle of treatment (Cycle 2 onwards), all of the following criteria must be met:

- ANC must be $\geq 1000/\text{mm}^3$ ($>750/\text{mm}^3$ if documented bone marrow involvement at study entry [Cycle 2 only]).
- Platelet count must be $\geq 75,000/\text{mm}^3$ ($>50,000/\text{mm}^3$ if documented bone marrow involvement [Cycle 2 only]).

NOTE: Patients with marrow involvement at study entry may start Cycle 2 with decreased ANC/platelet counts as documented above. For all other cycles, the standard criteria to start a new cycle apply.

- All other non-hematologic toxicity (except for alopecia, fatigue, and electrolyte/glucose abnormalities that are immediately reversible and/or not felt to be clinically significant) deemed at least possibly related to study therapy must have resolved to \leq Grade 1 or to the patient's baseline condition. Study therapy related fatigue must be resolved to \leq Grade 2.

Patients failing to meet these criteria may be delayed for up to 3 weeks (21 days) and should be restarted at adjusted dose levels as described below. Growth factors, platelet and blood transfusions may be used per institutional practice for all cycles except Cycle 1 of the phase 1 study (unless patient experiences a DLT).

6.5 Dose Delays & Modifications

All toxicities should be graded according to the National Cancer Institute (NCI) Common Terminology Criteria for Adverse Events Version 5.0 (CTCAE V5.0). A copy of the CTCAE V5.0 can be downloaded from the CTEP website (<http://www.ctep.cancer.gov>).

A +/-3 day window is allowed for scheduled ixazomib therapy, required tests and/or visits except as otherwise noted. Delays due to holidays, weekends, bad weather or other unforeseen circumstances will be permitted.

Patients who experience a dose delay during Cycle 1 of the phase 1 study shall be managed as described above in Section 6.2 and Section 6.2.1. If a patient experiences a DLT and continues on study therapy, follow the dose delays & modifications guidelines as noted in this section. **Phase I completed November 25, 2019.**

Patients on Cycle 2 and beyond of the phase I study and those enrolled on the phase II study shall not make up any ixazomib doses that are delayed >3 days due to toxicity. Missed doses can be taken as soon as the patient remembers if the next scheduled dose is 72 hours or more away, otherwise the dose shall be considered skipped and shall not be made up.

NOTE: It is the intent of this protocol to preserve the full labeled dosing of ibrutinib whenever possible. With the exception of the specified toxicities noted in Section 6.5.2, ibrutinib should be continued at full dose and on schedule for all patients, regardless of ixazomib delays or modifications. Patients who are unable to tolerate ixazomib at any dose level due to toxicity shall be removed from study therapy, except in cases of potential overlapping toxicity in which case the dose of ibrutinib may be reduced by one dose level (Table 6-6).

6.5.1 Dose Reductions/Modifications for Ixazomib and Ibrutinib

Table 6-3 Ixazomib and Ibrutinib Dose Adjustments for Hematologic Toxicities

Criteria	Action on Ixazomib	Action on Ibrutinib
Within-Cycle Dose Modifications		

 If platelet count $\leq 30 \times 10^9/L$ or ANC $\leq 0.50 \times 10^9/L$ on an ixazomib dosing day (other than Day 1). 	
 Ixazomib dose should be withheld. Complete blood count (CBC) with differential should be repeated at least twice weekly (with 2 days between CBC's) until ANC and/or platelet counts have exceeded the pre-specified values (Section 6.4) required to initiate a treatment cycle on at least 2 occasions. Upon recovery, ixazomib may be reinitiated with 1 dose level reduction (Table 6-5). 	
 If no recovery after reduction of ixazomib to 2.3 mg, then reduce ibrutinib to 420 mg dose. If no recovery on the 420 mg dose, then discontinue study therapy.
Dose Modifications for Subsequent Treatment Cycles		

 Delay of >2 weeks in the start of a subsequent cycle due to lack of toxicity recovery (Section 6.4). ANC $\leq 750 \times 10^9/L$ and/or platelet count $\leq 50 \times 10^9/L$ (except for Cycle 1 and Cycle 2; Section 6.4). NOTE: Patients requiring delay of ≤ 2 weeks before starting a cycle do not require a dose reduction unless a delay has been required on more than 1 cycle, in which case the ixazomib dose should be decreased by one level (Table 6-5). 	
 Hold ixazomib until resolution as per criteria in Section 6.4. Upon recovery, reduce ixazomib 1 dose level (Table 6-5). The maximum delay before treatment should be discontinued will be 3 weeks or at the discretion of the principal investigator. 	
 If no recovery after reduction of ixazomib to 2.3 mg, then reduce ibrutinib to 420 mg dose. If no recovery on the 420 mg dose, then discontinue study therapy.

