NOTE: Ibrutinib pre-treated patients must meet all eligibility criteria AND must have discontinued prior ibrutinib at least 3 months prior to starting study therapy.

Pretreated with ibrutinib: Yes No

If yes, does patient meet criteria above: Yes No

PHASE I COMPLETED NOVEMBER 25, 2019.

Phase II: Prior proteasome inhibitors allowed.

(Please note prior to Version 3.0 of the protocol prior proteasome inhibitor and/or Bruton's tyrosine kinase inhibitors were allowed but patients could not have been exposed to the combination of proteasome inhibitor and BTK inhibitor).

_____ 3.5 Age ≥ 18 years.

____ 3.6 ECOG performance status of 0-2 (Appendix I).

____ 3.7 Ability to understand and willingness to sign IRB-approved informed consent.

____ 3.8 Willing to provide archived tumor tissue, bone marrow (if sufficient bone marrow and tumor tissue are available) and blood samples for research (Section 13.0).

____ 3.9 Adequate organ function as measured by the following criteria, obtained \leq 2 weeks prior to registration:

- Absolute Neutrophil Count (ANC) \geq 750/mm³
ANC: _____ Date of Test: _____
- Platelets $>50,000/\text{mm}^3$
Platelets: _____ Date of Test: _____

NOTE: Platelet transfusions are not allowed within 3 days before registration to meet eligibility criteria.

- Serum Creatinine \leq 2x Upper Limit Normal (ULN)
Serum Creatinine: _____ ULN: _____ Date of Test: _____
- ALT and AST \leq 3x ULN
ALT: _____ Institution ULN: _____ Date of Test: _____
AST: _____ Institution ULN: _____ Date of Test: _____
- Total Bilirubin \leq 1.5x ULN (in the absence of previously diagnosed Gilbert's disease)
Total Bilirubin: _____ ULN: _____ Date of Test: _____

____ 3.10 Patients must not have received systemic treatment for MCL for at least 14 days prior to enrollment, except for steroids which may be used to manage acute symptoms related to disease up to 48 hours prior to starting study therapy. Radiation therapy must be concluded at least 14 days prior to enrollment.

____ 3.11 Women must not be pregnant or breastfeeding since we do not know the effects of ixazomib and ibrutinib on the fetus or breastfeeding child. All sexually active females of childbearing potential (not surgically sterilized and between menarche and 1 year post menopause) must have a blood test to rule out pregnancy within 2 weeks prior to registration.

Is the patient a woman of childbearing potential? _____ (yes/no)

If yes, Date of Test: _____ Results: _____

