Grade 3 Non-Hematologic Toxicity	
 Hold ixazomib until resolution to Grade \leq 1 or baseline. If not recovered to \leq Grade 1 or baseline within 2 weeks Subsequent recurrence Grade 3 that does not recover to \leq Grade 1 or baseline within 2 weeks Subsequent recurrence of Grade 3 toxicity that does not recover to \leq Grade 1 despite treatment at lowest dose level of ixazomib (GI toxicities ONLY) 	
 NONE NONE NONE For GI toxicities ONLY (nausea, vomiting, or diarrhea) reduce dose of ibrutinib to 420 mg daily. 	
See Section 6.5.2 for dose reductions/modifications for toxicities related to ibrutinib.
 
Monitor closely, take appropriate medical precautions, and provide appropriate symptomatic care.
 
In this setting, ibrutinib shall not be reduced below 420 mg daily. If a patient cannot tolerate the combination of ixazomib 2.3 mg and ibrutinib 420 mg, they shall be removed from study therapy.

Grade 4 Non-Hematologic Toxicity	
 Consider permanently discontinuing ixazomib. Discuss with PrECOG and principal investigator. If it is felt to be of potential clinical benefit to reinitiate therapy, patients should be managed per the Grade 3 non-hematologic toxicity guidelines above. 	
 NONE 	
See Section 6.5.2 for dose reductions/modifications for toxicities related to ibrutinib.
 
Exceptions are cases in which the investigator determines the patient is obtaining a clinical benefit.
 
Patients who experience a recurrent grade 4 non-hematologic toxicity shall be permanently removed from study therapy.

Patients requiring a delay of 2 weeks or less before starting a cycle do not require a dose reduction unless a delay has been required on more than 1 cycle, in which case the ixazomib dose should be decreased by one level (Table 6-5).

The maximum delay before treatment should be discontinued will be 3 weeks or at the discretion of the principal investigator.

Once ixazomib is reduced for any toxicity, the dose may not be re-escalated. If it is ultimately determined that therapy with ixazomib is no longer safe, the patient will be removed from the study.

Table 6-5 Recommended Dose Modifications for Ixazomib

	Starting Dose	Modification
Dose Level	4.0 mg	3.0 mg
Dose Level	3.0 mg	2.3 mg
Dose Level	2.3 mg	Remove from study

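### Table 6-3 prints the subsequent-cycle ANC trigger for reducing ixazomib as 750 × 10^9/L, 1000 times the 750/mm³ evidently meant

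*Protocol*

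**What the plan says.** Table 6-3 in Section 6.5.1 of the Protocol sets the haematologic rules for ixazomib and ibrutinib in two blocks.

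- **Within a cycle.** Ixazomib is withheld for platelets at or below 30 × 10^9/L, or for "ANC $\leq 0.50 \times 10^9/L$ on an ixazomib dosing day (other than Day 1".
- **Subsequent cycles.** The count trigger is "ANC $\leq 750 \times 10^9/L$ and/or platelet count $\leq 50 \times 10^9/L$ (except for Cycle 1 and Cycle 2; Section 6.4". The action is to hold ixazomib until the Section 6.4 criteria are met and then resume one dose level lower. A note in the same row says that patients delayed by 2 weeks or less "do not require a dose reduction unless a delay has been required on more than 1 cycle".

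The text before Table 6-5 makes any reduction permanent: "Once ixazomib is reduced for any toxicity, the dose may not be re-escalated".

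Section 6.4, which the row cites, works per mm³: "ANC must be $\geq 1000/\text{mm}^3$ ($>750/\text{mm}^3$ if documented bone marrow involvement at study entry [Cycle 2 only". Its platelet rule is 75,000/mm³, relaxed to above 50,000/mm³ for marrow involvement in Cycle 2. Its note adds: "For all other cycles, the standard criteria to start a new cycle apply".

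Eligibility criterion 3.9 is also per mm³: "Absolute Neutrophil Count (ANC) \geq 750/mm³" and "Platelets $>50,000/\text{mm}^3".

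Section 11.1.10.6 directs sites to Table 6-3 when neutropenia occurs.

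**The concern.** An ANC limit of 750 × 10^9/L is not a usable threshold, since any realistic neutrophil count lies below it. As printed, the row contradicts Section 6.4: a patient with an ANC above 1000/mm³ may start the cycle under Section 6.4, yet meets the Table 6-3 trigger to hold and reduce.

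The entry is an operative dosing rule. Its consequence lasts, because ixazomib is not re-escalated and Table 6-5 allows only 4.0, 3.0 and 2.3 mg before removal. Neutropenia is also expected with this treatment: Section 1.4.1.3 reports grade 3 or 4 neutropenia in 19 to 29% of patients on ibrutinib. Sites should therefore expect to consult this row.

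**Working it through.** **Conversion.** 1 L = 10^6 mm³, so 1 × 10^9/L = 10^9/10^6 = 1000/mm³.

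**All four count limits in Table 6-3:**

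| Block | Count | Printed (× 10^9/L) | Per mm³ | Plausible? |
|---|---|---|---|---|
| Within cycle | Platelets | 30 | 30 × 1000 = 30,000 | yes |
| Within cycle | ANC | 0.50 | 0.50 × 1000 = 500 | yes |
| Subsequent cycles | Platelets | 50 | 50 × 1000 = 50,000 | yes |
| Subsequent cycles | ANC | 750 | 750 × 1000 = 750,000 | **no** |

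Only the last entry fails, so this is not a notation used throughout the table.

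**Size of the slip.** Against 750/mm³: 750,000 / 750 = 1000. Against the Section 6.4 cycle-start minimum: 750,000 / 1000 = 750.

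**Which value was meant.** Three checks agree on 750/mm³ = 750/1000 = 0.75 × 10^9/L.

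1. *Pairing.* Criterion 3.9 sets ANC 750/mm³ beside platelets 50,000/mm³. Section 6.4 pairs 750 with 50,000 (Cycle 2, marrow involvement) and 1000 with 75,000 (otherwise). The Table 6-3 row carries 50 × 10^9/L = 50,000/mm³, which belongs with 750.
2. *Complement.* The relaxed Section 6.4 limits are above 750/mm³ and above 50,000/mm³. The Table 6-3 row uses at or below 750 and at or below 50 × 10^9/L. These are exact opposites once the ANC is read per mm³.
3. *Order.* 0.50 (within-cycle withholding) < 0.75 (reduction trigger) < 1.0 (cycle-start minimum), all × 10^9/L. The platelet limits run the same way: 30 < 50 < 75.

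**Literal reading.** The row excludes Cycles 1 and 2, so the printed trigger applies from Cycle 3. A patient with ANC 1000/mm³ has 1.0 × 10^9/L, which is at or below 750 × 10^9/L. The trigger is met although the Section 6.4 ANC criterion is also met. The hold would end at once, because it lasts only until Section 6.4 is satisfied, but the one-level reduction would remain.

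**Could text conversion explain it?** If the exponent had been 6, then 750 × 10^6/L = 750/mm³ and the line would be right. The platelet limit in the same line and both within-cycle limits read 10^9, and the neighbouring ANC entry keeps its decimal (0.50). A misread exponent is therefore unlikely, though it cannot be ruled out from the text alone.

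**The case against.** The strongest reply is that no clinician would act on a neutrophil limit of 750,000/mm³. The digits and the platelet limit beside them point to 750/mm³. Section 6.4 gives the cycle-start requirement in correct units, so the decision to delay a cycle does not depend on the misprinted figure; only the reduction trigger does. This stands, and it limits the practical effect. It does not make the entry correct, and nothing elsewhere in the Protocol corrects it.

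A reader might infer more, in three ways.

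- *That patients will be reduced wholesale from Cycle 3.* This follows from the literal text, but it is not a realistic prediction of what sites would do.
- *That sites could repair the entry in two ways, to 0.75 or to 1.0 × 10^9/L (the Section 6.4 value for these cycles), and so dose patients with ANC 751 to 999/mm³ differently.* The documents do not support this. No unit correction turns 750 into 1000, and 1.0 would break the pairing with platelets of 50 × 10^9/L. The note on delays of 2 weeks or less is also not tied to any ANC value, so if it spares such a patient a reduction under one repair, its wording does the same under the other.
- *That mixing per-mm³ and per-litre units is itself an error.* It is not. Limits that convert correctly are a matter of style.

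**Conclusion.** The ANC trigger in the subsequent-cycles row of Table 6-3 is wrong as printed, by a factor of 1000. The evident value is 0.75 × 10^9/L (750/mm³). It should be corrected because it is a dose-reduction threshold to which the Protocol sends sites, and the reduction it triggers is permanent.

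The practical consequence is probably small: the intended value can be recovered from criterion 3.9 and Section 6.4, and sites would likely do so. The exact binomial test of CR rate, its type I error, its power and the sample size of 31 eligible, treated patients do not use this figure and are unaffected.

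The conclusion assumes that the exponent in the available text is the one in the source document, which is likely given the other three entries in the table.

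**What to change.** In the subsequent-cycles row of Table 6-3, replace the ANC limit with ANC ≤0.75 × 10^9/L (750/mm³). Leave the platelet limit and the exception for Cycles 1 and 2 as they are.

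The cost is one table entry at the next amendment or clarification. Visits, laboratory tests, sample size and analysis do not change. Using one unit in Section 6.4 and Table 6-3 would be a convenience and is not needed for correctness.

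### Table 6-3 gives two answers on ixazomib dose from Cycle 3 for a patient with deep cytopenia at cycle start, on a first delay, who recovers within 2 weeks

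*Protocol*

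**What the plan says.** All references are to the Protocol.

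- **Section 6.4** sets the counts needed to start a cycle: ANC at least 1000/mm3 and platelets at least 75,000/mm3. Lower limits apply in Cycle 2 only, to patients with marrow involvement; "For all other cycles, the standard criteria to start a new cycle apply". Patients who miss the criteria may wait up to 3 weeks and "should be restarted at adjusted dose levels as described below".
- **Table 6-3, subsequent-cycles block, Criteria cell** lists two triggers: a start delayed by more than 2 weeks, and ANC of 750 or below and/or platelets of 50 x10^9/L or below ("except for Cycle 1 and Cycle 2; Section 6.4"). The Action column says to hold, then: "Upon recovery, reduce ixazomib 1 dose level (Table 6-5").
- **The NOTE in that same cell** concerns patients whose delay does not exceed 2 weeks. They, it says, "before starting a cycle do not require a dose reduction unless a delay has been required on more than 1 cycle". Where a further cycle is delayed, ixazomib drops one level.
- **The text after Table 6-4** repeats the waiver, again lifting it once a further cycle is delayed, and makes no exception for low counts. The sentence opens: "Patients requiring a delay of 2 weeks or less before starting a cycle do not require a dose reduction unless a delay has been".
- **Table 6-3, within-cycle block** deals with counts "on an ixazomib dosing day (other than Day 1"), with its own, lower limits.
- **Before Table 6-5** the protocol bars re-escalation of ixazomib once reduced. Table 6-5 runs 4.0 to 3.0 to 2.3 mg, then removal from study.

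**The concern.** The NOTE is not restricted to milder count shortfalls, and the low-count trigger is not restricted to long or repeated delays. One kind of patient falls under both, and the two lines point to different restart doses. Two investigators reading the same cell in good faith could treat that patient differently. A site that follows the NOTE can restart ixazomib at the unreduced dose after the more severe cytopenia for which the Action column orders a cut. A site that cuts the dose cannot reverse it.

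The ANC limit in the same cell is printed as 750 x10^9/L, which is not a usable threshold as it stands.

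**Working it through.** **Does the trigger always mean a delay?** From Cycle 3 a start needs ANC >=1000/mm3 and platelets >=75 x10^9/L. ANC <=750/mm3 lies inside <1000/mm3, and platelets <=50 lie inside <75 x10^9/L. A patient who meets the low-count trigger at cycle start is therefore always delayed, so the NOTE is always in play.

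The trigger does not print the words Day 1. That it covers the cycle start is inferred from the block title, the pointer to Section 6.4, and the within-cycle row, which excludes Day 1.

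**Which cases collide?** Take a patient from Cycle 3 who fails the start counts, and cross depth of count, length of delay, and first or repeat delay. Reading A treats the low-count line as an independent trigger. Reading B lets the NOTE override it.

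| Counts | Delay | First or repeat | Reading A | Reading B |
|---|---|---|---|---|
| Milder | <=2 weeks | First | No reduction | No reduction |
| Milder | <=2 weeks | Repeat | Reduce | Reduce |
| Milder | >2 weeks | First | Reduce | Reduce |
| Milder | >2 weeks | Repeat | Reduce | Reduce |
| <=750 and/or <=50 | <=2 weeks | First | **Reduce** | **No reduction** |
| <=750 and/or <=50 | <=2 weeks | Repeat | Reduce | Reduce |
| <=750 and/or <=50 | >2 weeks | First | Reduce | Reduce |
| <=750 and/or <=50 | >2 weeks | Repeat | Reduce | Reduce |

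One case in eight conflicts. Under Reading B, deleting the low-count trigger changes none of the eight outcomes, and the hold it orders is already imposed by Section 6.4. Reading B thus leaves the trigger with no function, which favors Reading A as the intent.

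**Does other text settle it?** Section 6.4 only points forward to the tables. Section 6.5.1.1 covers hematologic toxicity that has recovered in time for the next cycle, so it does not reach a delayed start. Sections 11.1.10.5 and 11.1.10.6 allow restart at a lower level but do not order it.

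**Size of the step** (three ixazomib doses per cycle, Table 6-5 levels):

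- 3 x 4.0 = 12 mg against 3 x 3.0 = 9 mg; (12 - 9)/12 = 25.0% less.
- 3 x 3.0 = 9 mg against 3 x 2.3 = 6.9 mg; (9 - 6.9)/9 = 23.3% less.
- At 2.3 mg the next printed step is removal from study.

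**Unit check.** 1 x10^9/L = 1000/mm3, so 750 x10^9/L = 750,000/mm3, and 750,000/750 = 1000 times the 750/mm3 used in Section 6.4. The within-cycle row prints its ANC limit correctly, as 0.50 x10^9/L.

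**CR design.** With 31 patients, rejection at 10 or more CRs, and rates of 21% and 40%, the exact binomial gives a type I error of 0.098 and power of 0.857. These agree with the stated 10% and 86%. The dosing rule does not enter this calculation.

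**The case against.** The strongest reply is that this is an ambiguity with a safe path through it. The NOTE says a reduction is not required; it does not forbid one. A site that reduces breaks neither line. The surrounding text leans the same way: Section 6.4 speaks of restarting at adjusted doses, Section 6.5.1.1 lets severity alone drive a reduction without any delay, and Section 11.1.10 mentions restart at a lower level. All of this stands, and it supports reduction as the intent. It does not help the site that keeps the dose, which follows the NOTE while departing from the Action column. None of these places states precedence.

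A reader might infer that for a patient already at 2.3 mg the unclear line simply decides between continuing and removal. The documents do not support that.

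- Section 6.5 makes an exception to removal for potentially overlapping toxicity and allows a one-level ibrutinib reduction instead. Cytopenias are listed for ibrutinib too (Sections 1.4.1.3 and 11.2.9.3).
- The ibrutinib column of Table 6-3 also offers 420 mg, though only where counts do not recover, so it does not clearly cover this patient.
- The route to 2.3 mg without a prior cycle delay is two within-cycle cuts ("Upon recovery, ixazomib may be reinitiated with 1 dose level reduction (Table 6-5")). It depends largely on counts that Phase II does not mandate: Section 10 requires labs on Cycle 1 Days 1 and 15, Day 1 of Cycles 2 to 7, and every third cycle after that.

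The same schedule limits how often a qualifying count at cycle start would be seen.

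A reader might also infer from the unit slip that every patient meets the trigger. Literally they would, but Section 6.4 supplies the usable figure, and no site is likely to apply 750,000/mm3. It is a correction to make, with no separate dosing consequence shown.

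**Conclusion.** The point holds in one defined case: from Cycle 3, ANC <=750/mm3 and/or platelets <=50 x10^9/L at cycle start, a first delay, and recovery within 2 weeks. The table then both orders a one-level reduction and says none is required. Reduction is the likely intent but is not written.

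The effect on a patient is one irreversible ixazomib step of 25% or 23%, arising at most once, since a second delay leads to reduction on any reading. At 2.3 mg the printed outcome is removal, subject to the Section 6.5 exception. The protocol gives no frequency, so no trial-level effect can be stated, and the CR design figures are untouched.

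This rests on two readings: that the low-count trigger applies at cycle start, and that the ANC limit means 750/mm3. It is worth correcting because sites apply this table directly. It is not a flaw in the primary analysis.

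**What to change.** Reword the NOTE in Table 6-3, and the matching sentence after Table 6-4 where the delay is hematologic, along these lines: *A cycle start delayed by no more than 2 weeks needs no ixazomib reduction if no other cycle has been delayed and, from Cycle 3, ANC stayed above 750/mm3 and platelets above 50 x10^9/L on the scheduled Day 1 and throughout the delay. Otherwise reduce ixazomib one level (Table 6-5).*

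Do not narrow the low-count trigger itself to Day 1. A patient with ANC 900/mm3 on Day 1 who falls to 600/mm3 during the hold and recovers within 2 weeks would then have no reduction trigger on a first delay. The within-cycle row covers only dosing days other than Day 1, and Section 6.5.1.1 covers only toxicity that has recovered in time.

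Print the ANC limit as 750/mm3 (0.75 x10^9/L).

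The cost is one table cell and one sentence, in the next amendment or a clarification letter, with no new data or visits. The downside is that a few patients with brief deep cytopenia will drop one level who might otherwise have kept their dose. If the sponsor would rather have the waiver govern, the table should say so outright.
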